Study design		Using a traditional "3+3" dose-escalation design, subjects will be sequentially assigned to one of three dose groups (2.8×10^{10} units, 1.4×10^{11} units, and 7.0×10^{11} units per dose, once daily, with continuous intranasal instillation for 4 days). Each dose group will include 3 subjects, who will be enrolled one by one. The exploration of the next dose can only proceed if no dose-limiting toxicity (DLT) is observed in the 3 subjects. If 1 out of the 3 subjects experiences DLT, an additional 3 subjects will be enrolled in the same dose group; the exploration of the next dose can only move forward if no DLT is observed in these newly added 3 subjects. A minimum of 6 and a maximum of 18 subjects will be recruited during the dose exploration phase. Patients will receive other standard medical treatments in accordance with the recommendations in the 2022 Chinese Guidelines for Secondary Prevention of Ischemic Stroke and Transient Ischemic Attack , including antiplatelet drugs or anticoagulants, antihypertensive drugs, lipid-lowering drugs, and glucose-lowering drugs.
Outcome Measures	Primary Outcome Measure	Dose-Limiting Toxicity (DLT) Related to hUC-MSC-sEV-001 Includes: (1) Grade 3-4 severe adverse events occurring on day 14 (+-2), graded according to Common Terminology Criteria for Adverse Events (CTCAE) V5.0; (2) NIHSS score increase of ≥ 4 from baseline on day 14 (+-2); NIHSS score assessed by a professional rehabilitation physician;(3) Symptomatic intracranial hemorrhage occurring on day 14 (+-2); detected via CT scan and patient symptom presentation.
	Secondary Outcome Measures:	Serious adverse events related to the investigational drug within 90 (+-7) days. Distribution of Modified Rankin Scale (mRS) Scores within 90 (+-7) days. Barthel Index within 90 (± 7) days. Five-level, five-dimensional EuroQol (EQ-5D-5L) . Proportion of Modified Rankin Scale (mRS) Scores of 0-2 within 90 (+-7) days. All-cause mortality at 90 (+-7) days. Changes in infarct volume at 14 (+-2) days compared to baseline. Change from Baseline in National Institutes of Health Stroke Scale (NIHSS) Score.
Follow-up duration		Baseline (0~1 day), 7 (± 1) days, 14 (± 2) days, 90 (± 7) days
Sample size		6-18 subjects need to be included.

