 - **Hematology:** Complete blood count (CBC) with differential (red blood cell [RBC], hemoglobin [Hb], white blood cell [WBC], neutrophil percentage [NEUT%], lymphocyte percentage [LYMPH%], platelet count [PLT]);
 - **Clinical Chemistry:** Liver function (ALT, AST, total bilirubin [TBIL], alkaline phosphatase [ALP], γ -glutamyl transferase [γ -GT]), renal function

(Scr, BUN), fasting blood glucose (FBG), glycated hemoglobin (HbA1c), lipid profile (total cholesterol [TC], triglycerides [TG], HDL, LDL, lipoprotein (a) [LP(a)]);

- **Coagulation Function:** PT, INR, APTT, thrombin time (TT), fibrinogen (FIB);
- **Serum Electrolytes:** Potassium (K⁺), sodium (Na⁺), calcium (Ca²⁺), magnesium (Mg²⁺), phosphorus (P³⁺), chlorine (Cl⁻);
- **Infectious Disease Screening:** HBsAg, hepatitis B surface antibody (HBsAb), hepatitis B e antigen (HBeAg), hepatitis B e antibody (HBeAb), hepatitis B core antibody (HBcAb), HCV antibody, HIV antibody, TPPA, RPR;
- **Tumor Markers:** Alpha-fetoprotein (AFP), carbohydrate antigen 199 (CA199), carcinoembryonic antigen (CEA);
- **Urinalysis:** Urine protein (PRO), urine glucose (GLU), quantitative urine RBC, quantitative urine WBC, urine ketones (KET);
- **Pregnancy Test:** Urine pregnancy test for women of childbearing potential at screening and Day 90.

3. Imaging Examinations:

- **Chest X-ray:** Performed at screening and Day 90 (to exclude active pulmonary infection or malignancy);
- **Electrocardiogram (ECG):** 12-lead ECG performed at screening, Day 14, and Day 90 (to evaluate cardiac function and detect arrhythmias);
- **Cerebral Imaging:**
 - Baseline: NCCT, DWI, MRA/CTA (to confirm infarct location and vascular occlusion);
 - Day 14 and Day 90: DWI, fluid-attenuated inversion recovery (FLAIR), CTA/CT perfusion (CTP) (to assess infarct volume, edema, and cerebral perfusion).

4. Adverse Events Monitoring:

- AEs are monitored from the time of informed consent signing until 30 days after the last dose of the study drug.
- All AEs (including nasal irritation, headache, rash) are documented in the "Adverse

Event Record Form" in the CRF, with details including onset time, severity (CTCAE V5.0), duration, relationship to the study drug (definite, probable, possible, unlikely, unrelated), treatment measures, and outcome.

- SAEs are reported to the Ethics Committee, sponsor, and NMPA in accordance with regulatory requirements (within 24 hours of awareness).

(3) Efficacy Observation Indicators

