1. Neurological Function Scales:

- **NIHSS:** Assesses the severity of neurological deficits (range: 0-42; higher scores indicate more severe deficits). Administered at baseline, Day 7, Day 14, and Day 90.
- **mRS:** Assesses functional independence (range: 0-6; scores 0-2 indicate good functional outcome). Administered at baseline, Day 7, Day 14, and Day 90.
- **Modified Barthel Index (MBI):** Assesses activities of daily living (range: 0-100; higher scores indicate better independence). Administered at baseline, Day 14, and Day 90.
- **EQ-5D-5L:** Assesses health-related quality of life (including mobility, self-care, usual activities, pain/discomfort, anxiety/depression; scored as a utility value ranging from -0.291 to 1.0). Administered at baseline, Day 14, and Day 90.

2. Cerebral Perfusion Parameters (CTP):

- Measured at baseline, Day 14, and Day 90: cerebral blood volume (CBV), cerebral blood flow (CBF), mean transit time (MTT), time to peak (TTP) in the infarct core and penumbra.
- Changes in perfusion parameters from baseline are used to evaluate the improvement of cerebral blood flow.

3. Infarct Volume Measurement:

- Infarct volume is measured on DWI using the ABC/2 method (A: maximum length, B: maximum width perpendicular to A, C: number of slices × slice thickness).
- Changes in infarct volume from baseline to Day 14 are used to evaluate infarct progression or regression.

5. Outcome Evaluation Indicators

(1) Primary Safety Endpoints

- **Dose-Limiting Toxicity (DLT):** Assessed within 14 days of the first dose, defined as any of the following:
 1. Grade 3-4 AE related to the study drug (CTCAE V5.0), such as severe nasal bleeding, anaphylactic reaction, or hepatic injury;
 2. Increase in NIHSS score ≥ 4 points from baseline (indicating significant neurological deterioration);
 3. Symptomatic intracranial hemorrhage (confirmed by CT/MRI and associated with neurological deterioration).

(2) Secondary Safety Endpoints

1. **SAE Incidence:** Proportion of subjects with drug-related SAEs within 90 days of the first dose;
2. **All-Cause Mortality:** Proportion of subjects who die from any cause within 90 days of the first dose;
3. **Laboratory Abnormality Rate:** Proportion of subjects with Grade ≥ 3 laboratory abnormalities (e.g., thrombocytopenia, elevated liver enzymes) within 90 days.

(3) Efficacy Endpoints

1. **Functional Outcome:** Proportion of subjects with mRS score 0-2 at Day 90;

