2. Efficacy Assessments:

- Neurological scales: NIHSS, mRS, MBI, EQ-5D-5L;
- Infarct volume measurement (DWI) and CTP parameter analysis.

3. Documentation: Record combined medications, rehabilitation therapy, and schedule the Day 90 visit.

Fourth Visit (Day 90 ± 7)

1. Safety Assessments:

- Vital signs measurement;
- Laboratory tests: CBC, clinical chemistry, coagulation function, serum electrolytes, infectious disease screening, tumor markers, urinalysis, pregnancy test (if applicable);
- Imaging examinations: Chest X-ray, 12-lead ECG, DWI, FLAIR, CTA/CTP;
- Final AE follow-up (until 30 days after the last dose).

2. Efficacy Assessments:

- Neurological scales: NIHSS, mRS, MBI, EQ-5D-5L;
- Final infarct volume measurement and CTP parameter analysis.

3. Study Completion: Confirm completion of all assessments, and document any protocol deviations.

Items/Visits	Baseline (Day 0)	Day 7 (±1)	Day 14 (±2)	Day 90 (±7)
Sign Informed Consent Form	●			
Review Inclusion/Exclusion Criteria	●			
Collect Demographic & Clinical Data	●	●	●	●
Vital Signs	●	●	●	●
Urine Pregnancy Test	●			●
Hematology (CBC) *	●	●	●	●
Clinical Chemistry (Liver/Kidney Function, Glucose, Lipids) *	●	●	●	●
Coagulation Function (PT, INR, APTT, FIB)	●		●	●
Serum Electrolytes	●		●	●
Infectious Disease Screening (8 Items)	●		●	●
Tumor Markers (AFP, CA199, CEA) *	●		●	●
Urinalysis *	●	●	●	●

Items/Visits	Baseline (Day 0)	Day 7 (±1)	Day 14 (±2)	Day 90 (±7)
Chest X-ray	•		•	
12-Lead ECG	•		•	•
Cerebral Imaging (CT/MRI/CTA/CTP)	•	•	•	•
Neurological Scales (NIHSS, mRS)	•	•	•	•
Modified Barthel Index (MBI)	•		•	•
EQ-5D-5L Score	•		•	•
Record Adverse Events	•	•	•	•
Record Concomitant Medications	•	•	•	•
Record Rehabilitation Therapy	•	•	•	•

7. Regulations for Packaging, Acceptance, Storage, Distribution, and Recovery of Study MSC-sEV Preparations

(1) Packaging of Study MSC-sEV Preparations

- **Primary Packaging:** Sterile glass vials (2.0 mL) with rubber stoppers and aluminum caps, labeled with the study drug name, batch number, dose level, expiration date, storage conditions, and "For Clinical Trial Use Only".
- **Secondary Packaging:** Individual cartons containing one vial of study drug and one vial of hyaluronidase, with a leaflet describing the administration method.
- **Tertiary Packaging:** Insulated containers with dry ice for transportation, labeled with "Biological

Product", "Keep Frozen (-80°C)", and the sponsor's contact information.

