
- **Recovery Procedures:**

1. The CRC labels the recoverable study drug with "To Be Recovered" and records the reason in the inventory log;
2. The study drug is returned to the sponsor in insulated containers with dry ice, accompanied by a "Study Drug Recovery Form";
3. The sponsor confirms receipt and issues a "Recovery Confirmation Certificate", which is stored in the study file.

8. Observation and Management of Adverse Events

(1) Definitions

- **Adverse Event (AE):** Any untoward medical occurrence in a subject administered a pharmaceutical product, which does not necessarily have a causal relationship with this treatment. AEs include clinical signs (e.g., abnormal laboratory findings), symptoms, or diseases.
- **Serious Adverse Event (SAE):** An AE that results in death, is life-threatening, requires inpatient hospitalization or prolongation of existing hospitalization, causes persistent or significant disability/incapacity, or is a congenital anomaly/birth defect.
- **Adverse Drug Reaction (ADR):** A response to a drug that is noxious and unintended, and which occurs at doses normally used in humans for the prophylaxis, diagnosis, or therapy of diseases, or for the modification of physiological function.
- **Dose-Limiting Toxicity (DLT):** An AE that is severe enough to prevent dose escalation, as defined in Section 5.1 (Primary Safety Endpoints).

(2) Observation and Recording of Adverse Events

- **Monitoring Period:** From the time of informed consent signing until 30 days after the last dose of the study drug.
- **Reporting Requirements:** Subjects are instructed to report any new symptoms, signs, or discomfort to the investigator immediately. The investigator queries the subject about AEs at each visit using open-ended questions (e.g., "Have you experienced any new symptoms since your last visit?").
- **Documentation:** All AEs are recorded in the "Adverse Event Record Form" in the CRF, including:
 - Onset time, date, and duration;

- Severity (CTCAE V5.0: Grade 1 = mild, Grade 2 = moderate, Grade 3 = severe, Grade 4 = life-threatening, Grade 5 = death);
- Description of signs and symptoms (e.g., "nasal congestion, mild, lasting 2 days");
- Relationship to the study drug (assessed using the five-point scale: definite, probable, possible, unlikely, unrelated);
- Treatment measures (e.g., "normal saline nasal irrigation");
- Outcome (resolved, resolving, stable, worsening, fatal).

(3) Management of Adverse Events

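### Adverse event monitoring is stated to end about Day 33, but drug-related SAEs are a secondary endpoint to Day 90, and the recording rules conflict on Days 34-90

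*Protocol*

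**What the plan says.** Three places in the protocol set the same limit on AE monitoring:

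- Section 4(2), item 4: "AEs are monitored from the time of informed consent signing until 30 days after the last dose of the study drug".
- Section 8(2), Monitoring Period: "From the time of informed consent signing until 30 days after the last dose of the study drug".
- Section 6, Fourth Visit (Day 90 ± 7), Safety Assessments: "Final AE follow-up (until 30 days after the last dose".

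Two places define an endpoint that runs well past that limit:

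- Section 5(2), Secondary Safety Endpoints: "Proportion of subjects with drug-related SAEs within 90 days of the first dose".
- Synopsis, Secondary Outcome Measures: "Serious adverse events related to the investigational drug within 90 (+-7) days".

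Section 8(1) makes an SAE a subset of AEs ("An AE that results in death, is life-threatening, requires inpatient hospitalization", and so on). No section gives SAEs a collection period of their own.

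Three other rules carry no 30-day limit:

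- The Section 6 schedule table has a row "Record Adverse Events" that is ticked at Day 90.
- Section 8(2), Reporting Requirements: "The investigator queries the subject about AEs at each visit using open-ended questions".
- Section 8(5) requires SAE reports within 24 hours of awareness and gives no end date.

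**The concern.** An endpoint can be computed only from data that are collected over its whole window. Read as written, the AE limit stops collection at about Day 33, while the SAE endpoint counts events to Day 90.

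No visit falls between Day 14 and Day 90. The Day 90 visit is therefore the only scheduled occasion for asking about an SAE that arose on Days 34-90, and it is in the text for that visit that the 30-day limit is repeated. Staff who follow the visit text and staff who follow the schedule table would record different events for the same subject.

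At stake is the 90-day drug-related SAE proportion, in a safety trial of 6 to 18 subjects where a single event moves the result visibly.

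**Working it through.** The protocol states no figure for this gap, so there is none to reproduce. The check is day arithmetic.

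**Inputs**

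- Last dose: Day 3 (Section 3(2), dosing on Days 0 to 3). The synopsis treatment plan can be read as putting the last dose on Day 4.
- AE limit: last dose + 30 days (Sections 4(2), 8(2) and Fourth Visit).
- End of the SAE endpoint: Day 90 (Section 5(2)), or Day 83 to 97 with the synopsis window of ±7 days.
- Visits: baseline, Day 7 (±1), Day 14 (±2) and Day 90 (±7).

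**Days outside the AE window**

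End of AE window = last dose day + 30. Days not covered = endpoint end − end of AE window.

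| Last dose | AE window ends | Endpoint ends | Days not covered | Share |
|---|---|---|---|---|
| Day 3 | 3 + 30 = Day 33 | Day 90 | 90 − 33 = 57 | 57/90 = 63.3% |
| Day 3 | Day 33 | Day 83 | 83 − 33 = 50 | 50/83 = 60.2% |
| Day 3 | Day 33 | Day 97 | 97 − 33 = 64 | 64/97 = 66.0% |
| Day 4 | 4 + 30 = Day 34 | Day 90 | 90 − 34 = 56 | 56/90 = 62.2% |
| Day 0 only (dosing stopped) | 0 + 30 = Day 30 | Day 90 | 90 − 30 = 60 | 60/90 = 66.7% |

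**Gap between visits**

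- Nominal: 90 − 14 = 76 days.
- Shortest: 83 − 16 = 67 days.
- Longest: 97 − 12 = 85 days.

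The Day 90 visit takes place on Day 83 at the earliest, 83 − 33 = 50 days after the stated window has closed.

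**Weight of one event**

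One unrecorded drug-related SAE shifts the overall proportion by 1/18 = 5.6 percentage points with 18 subjects and by 1/6 = 16.7 points with 6.

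**Which rules reach an SAE with onset on Days 34-90**

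| Rule | Covers a new SAE on Days 34-90? |
|---|---|
| 4(2) and 8(2), monitoring period | No |
| 6, Fourth Visit text | No |
| 6, schedule table, AE row at Day 90 | Yes |
| 8(2), AE question at each visit | Yes |
| 8(5), 24-hour SAE report | Only if the investigator learns of it |
| 8(3) and 8(6), follow-up to resolution | No; concerns events already recorded |

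Section 8(2) holds both the limit and the each-visit question, and nothing says which takes precedence.

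**The case against.** The strongest reply is that late SAEs would be picked up anyway.

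- The sample question in Section 8(2) asks about new symptoms since the previous visit. At Day 90 that reaches back to Day 14, and the table ticks AE recording at that visit.
- Subjects are told to report symptoms at once, and concurrent diseases have their own form with no Day 33 cut-off (Section 3(4)).
- The SAE form in Section 8(5) includes causality, so any SAE that becomes known is assessed.
- The limit can be read as applying to general AE monitoring only, because Section 4(2) gives SAEs a separate bullet.
- The Day 90 wording may mean closing out events that began within the window.

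These points rule out any claim that no SAE is collected after Day 33. They do not remove the stated limit, which appears three times and makes no exception for SAEs. Reporting on awareness does not oblige anyone to look for events.

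A second reply is that few late SAEs could count as drug-related. Section 8(4) ties the temporal factor to onset within the exposure period, and rechallenge is not applicable. If exposure means the dosing days, at most two or three of the five factors could support causality, giving unlikely or at best possible. This bears on the likely number of events, but the exposure period is not defined, and an event that is never recorded is never assessed.

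The third reply is that calendar shares do not measure impact. That stands: 63% is a share of days, not of SAEs.

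**Conclusion.** The contradiction is real. The protocol states an AE window that closes at about Day 33 and an SAE endpoint that runs to Day 90, and its recording rules disagree about the interval between them. On the main text's dosing days, 57 of 90 days (63%) fall outside the window. The share is 60% to 66% across the ±7-day endpoint window, and 62% if the last dose is on Day 4. Dosing stopped after Day 0 would make it 67%.

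This rests on reading the AE limit as covering SAEs, which follows from the protocol's own definition of an SAE. The consequence is uncertain capture and a possible undercount of one secondary endpoint. The number of SAEs missed cannot be estimated.

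Not affected are the 14-day dose-limiting toxicity endpoint, escalation and the two-event stopping rule, all-cause mortality, and the Grade 3 or higher laboratory endpoint, whose tests are scheduled at Day 90. Imaging, ECG and scales at Day 90 may show some late harm, but they do not by themselves record an SAE or its relation to the study drug. It should be fixed, but it does not undermine the trial's primary purpose.

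**What to change.** Reconcile Section 4(2) item 4, Section 8(2) and the Fourth Visit text with Section 5(2), the synopsis and the schedule table. State in each that SAEs are recorded, with causality assessment, through the Day 90 (±7) visit. If non-serious AEs are to keep the limit of 30 days after the last dose, say so separately and mark it in the schedule table. The days of the SAE endpoint left outside the collection window then fall from 57 to 0.

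The cost is protocol wording in three places, the table mark if the shorter limit is kept, and a few more CRF entries at a visit that already takes place. No visit or procedure is added, and the sample size does not change.

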Single-center, prospective, dose-escalation clinical trial.

(2) Trial Administration Strategy

A traditional "3+3" dose-escalation design will be adopted. Subjects will be sequentially assigned to one of three dose groups (2×10^{10} units, 1×10^{11} units, 5×10^{11} units per administration, once daily for 4 consecutive days via intranasal instillation). Each dose group initially enrolls 3 subjects, with sequential enrollment (i.e., the next subject is enrolled only after the previous subject completes the 14-day DLT observation period).

- If no DLT is observed in 3 subjects of a dose group, the study proceeds to the next higher dose level.

- If 1 out of 3 subjects experiences DLT, an additional 3 subjects are enrolled in the same dose group. If no DLT is observed in the additional 3 subjects, the study proceeds to the next higher dose level; if ≥ 1 additional subject experiences DLT, the current dose level is defined as the maximum tolerated dose (MTD), and dose escalation is terminated.
- A total of 6 to 18 subjects will be recruited during the dose-escalation phase.

(3) Study Suspension or Early Termination

The study will be suspended or terminated early if any of the following occurs:

- Violation of the *Good Clinical Practice (GCP)* or the *Administrative Measures for Stem Cell Clinical Research (Trial)*;
- Emergence of new safety or efficacy data on MSC-sEVs indicating that the trial poses a serious risk to patient safety or is clearly ineffective;
- Failure to enroll subjects as scheduled for 3 consecutive months;
- Major protocol deviations that affect the validity of study data;
- Request for termination by the sponsor or regulatory authorities.

2. Subject Selection Criteria

(1) Inclusion Criteria

- Confirmed diagnosis of acute ischemic stroke (in accordance with the *Chinese Guidelines for the Diagnosis and Treatment of Acute Ischemic Stroke (2023)*);
- Aged 18-70 years, regardless of gender;
- Anterior circulation occlusion (internal carotid artery, middle cerebral artery M1/M2 segment) confirmed by CTA or MRA;
- mRS score of 0-1 before the current stroke episode (indicating no or minimal disability prior to the index event);
- ASPECTS ≥ 6 on non-contrast computed tomography (NCCT) or diffusion-weighted imaging (DWI) after stroke onset (indicating a small to moderate infarct volume);
- NIHSS score ≥ 6 at screening (indicating moderate to severe neurological deficit);

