2. **Neurological Improvement:** Mean change in NIHSS score from baseline to Day 14 and Day 90; proportion of subjects with NIHSS score reduction ≥ 4 points at Day 14;
3. **Functional Independence:** Mean change in MBI score from baseline to Day 90; proportion of subjects with MBI score ≥ 60 (indicating moderate independence) at Day 90;
4. **Quality of Life:** Mean change in EQ-5D-5L utility value from baseline to Day 90.

(4) Exploratory Endpoints

1. **Infarct Volume Change:** Mean change in infarct volume from baseline to Day 14;
2. **Cerebral Perfusion Improvement:** Mean changes in CBF, CBV, MTT, and TTP from baseline to Day 14;
3. **Correlation Analysis:** Correlation between baseline characteristics (e.g., age, NIHSS score) and efficacy outcomes.

6. Study Protocol Flow and Evaluation Indicators

First Visit [Baseline (Day 0)]

1. **Informed Consent:** The investigator explains the study protocol to the subject/legal representative, who signs the informed consent form if willing to participate.
2. **Screening Assessments:**
 - Demographic and clinical data collection;
 - Vital signs measurement;
 - Laboratory tests: CBC, clinical chemistry, coagulation function, serum electrolytes, infectious disease screening, tumor markers, urinalysis, pregnancy test (if applicable);
 - Imaging examinations: NCCT, DWI, MRA/CTA, chest X-ray, 12-lead ECG;
 - Neurological scales: NIHSS, mRS, MBI, EQ-5D-5L.
3. **Eligibility Confirmation:** The investigator reviews the inclusion/exclusion criteria and confirms eligibility.
4. **Study Drug Administration:**
 - Nasal mucosa pretreatment with hyaluronidase (150 U per nostril);
 - Instill the first dose of hUC-MSC-sEV-001;
 - Measure vital signs 30 minutes after administration.
5. **Documentation:** Record combined medications, rehabilitation therapy plans, and any AEs.

Second Visit (Day 7 ± 1)

1. **Safety Assessments:**
 - Vital signs measurement;
 - Laboratory tests: CBC, clinical chemistry, urinalysis;
 - AE monitoring and recording.
2. **Efficacy Assessments:**
 - Neurological scales: NIHSS, mRS.
3. **Documentation:** Record combined medications and rehabilitation therapy progress.

Third Visit (Day 14 ± 2)

1. Safety Assessments:

- Vital signs measurement;
- Laboratory tests: CBC, clinical chemistry, coagulation function, serum electrolytes, infectious disease screening, tumor markers, urinalysis;
- Imaging examinations: 12-lead ECG, DWI, FLAIR, CTA/CTP;
- AE monitoring and recording (including SAE follow-up).

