 - Grade ≥ 3 laboratory abnormalities are summarized as frequency (percentage) by dose group.

(4) Sample Size Justification

This is a phase I dose-escalation study designed to explore the safety and MTD of hUC-MSC-sEV-001. Using the "3+3" design, a sample size of 6-18 subjects is sufficient to identify the MTD with a 90% probability of avoiding overdosing and a 80% probability of identifying the MTD if it exists.

(5) Statistical Software

All statistical analyses are performed using SAS 9.4 software (SAS Institute Inc., Cary, NC, USA). Two-sided tests are used, and a P-value < 0.05 is considered statistically significant.

(6) Interim Analysis

No interim analysis is planned for this study due to the small sample size. The study will be terminated early only if safety concerns arise (e.g., ≥ 2 subjects experience DLT at the same dose level).

12. Quality Control and Assurance

(1) Protocol Compliance

- **Training:** All study personnel (investigator, CRC, monitor, pharmacist) receive training on the study

protocol, GCP, and stem cell clinical research regulations before study initiation. Training records are retained in the study file.

- **Standard Operating Procedures (SOPs):** SOPs are developed for key processes, including subject screening, study drug administration, adverse event reporting, and data management. Study personnel strictly follow the SOPs to ensure consistency.
- **Protocol Deviation Monitoring:** The monitor records all protocol deviations (e.g., missed visits, incorrect dose administration) in the "Protocol Deviation Log". Major deviations are reported to the Ethics Committee and sponsor.

(2) Study Drug Quality Control

- **Manufacturing Quality:** The study drug is produced under GMP conditions, and each batch is tested for purity, potency, sterility, and endotoxin levels. A certificate of analysis (CoA) is provided for each batch.
- **Storage and Transportation:** Temperature monitoring during transportation and storage ensures that the study drug remains within the specified temperature range (-80°C ± 10°C). Temperature records are reviewed and archived.
- **Inventory Management:** The study drug inventory is checked monthly to ensure that the quantity administered matches the quantity received, and to prevent expiration or loss.

(3) Laboratory Quality Control

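### The ABC/2 rule for infarct volume takes lesion height from slice thickness rather than slice spacing, and slice geometry is not held constant between visits

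*Protocol*

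**What the plan says.** Protocol section 4(3), item 3 (Infarct Volume Measurement), fixes the method on DWI: "using the ABC/2 method (A: maximum length, B: maximum width perpendicular to A, C: number of slices × slice thickness". The same item states the use: "Changes in infarct volume from baseline to Day 14 are used to evaluate infarct progression or regression".

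The status of the endpoint differs by place. The synopsis lists "Changes in infarct volume at 14 (+-2) days compared to baseline" among the secondary outcome measures. Section 5(4) lists "Mean change in infarct volume from baseline to Day 14" as an exploratory endpoint. Section 6 repeats the measurement at Day 90.

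The imaging schedule in section 4(2), item 3, has DWI at both ends of the comparison: "Baseline: NCCT, DWI, MRA/CTA (to confirm infarct location and vascular occlusion" and "Day 14 and Day 90: DWI, fluid-attenuated inversion recovery (FLAIR), CTA/CT perfusion (CTP". It gives no slice thickness and no inter-slice gap, and it does not say that the acquisition is to be the same at each visit. Section 4(3) does not say how to treat several separate lesions.

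**The concern.** The extent of a lesion across slices is the number of slices times the distance between slice centres, that is, thickness plus gap. Number of slices times thickness equals this only when the gap is zero. On a scan with a gap, the written rule gives too small a volume.

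ABC/2 is also an approximation with one fixed shape coefficient. The subjects have ICA or MCA M1/M2 occlusions (section 2(1)), and nothing ensures that their infarcts share one shape or keep it for 14 days.

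At stake is the reading of the Day 14 change as progression or regression in dose groups of 3 or 6 subjects, where an error in one or two scans does not average out. The rule stands in the protocol itself. If only A, B and C are recorded under it, a later correction means going back to the images.

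**Working it through.** The protocol states no figure that depends on infarct volume (no SD, expected change or measurement error), so there is nothing to reproduce. The check is geometric. **All values for thickness t, gap g and lesion shape are assumptions.**

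**1. Gap, single scan.** Stated C divided by actual height is approximately n·t / [n·(t+g)] = t/(t+g). For t = 5 mm:

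| Gap g (mm) | t/(t+g) | Volume too small by | ABC/2 for A = 6, B = 4, height 5 cm |
|---|---|---|---|
| 0 | 1.000 | 0% | 60.0 mL |
| 0.5 | 0.909 | 9.1% | 54.5 mL |
| 1.0 | 0.833 | 16.7% | 50.0 mL |
| 1.5 | 0.769 | 23.1% | 46.2 mL |

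The last column is 6 × 4 × (5 × factor) / 2. A true ellipsoid of these dimensions has volume π/6 × 6 × 4 × 5 = 62.8 mL.

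**2. Gap, same geometry at both visits.** The factor multiplies both volumes. Take t = 5, g = 1.5 and a fall from 40 to 30 mL:
- absolute change: −10 × 0.769 = −7.7 mL instead of −10 mL;
- percent change: −25% either way.

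The absolute change shrinks, its direction does not alter, and a zero change stays zero.

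**3. Gap, geometry differing between visits, true change zero.** Apparent change = (factor at Day 14 / factor at baseline) − 1. For t = 5 mm:
- 1.0 to 1.5 mm: 0.769/0.833 − 1 = −7.7%;
- 0 to 1.0 mm: −16.7%;
- 0 to 1.5 mm: −23.1% (60.0 to 46.2 mL in the table, a false fall of 13.8 mL);
- 1.5 to 0 mm: +30.0%.

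**4. Shape, single scan.** If the true volume is k·A·B·C, then ABC/2 divided by the true volume is 0.5/k.

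| Shape | k | Error of ABC/2 |
|---|---|---|
| Triangular prism | 1/2 | 0% |
| Ellipsoid | π/6 = 0.524 | −4.5% |
| Elliptic cylinder | π/4 = 0.785 | −36.3% |
| Elliptic cone | π/12 = 0.262 | +91.0% |

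**5. Shape, change over time.** A constant k cancels in one subject's percent change. If k moves from 0.52 to 0.45 with true volume unchanged, the apparent change is 0.52/0.45 − 1 = +15.6%. A true fall of 13.5% (0.45/0.52 − 1) would then read as no change.

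**6. Shape, group mean of absolute changes.** Section 5(4) specifies a mean change and does not say percent, so it is read here as absolute. Factors that are constant within each subject but differ between subjects do not cancel in such a mean. Constructed example: true changes of −10, +6 and +6 mL have mean +0.67 mL. If the lesions keep the shapes triangular prism, ellipsoid and elliptic cylinder (factors 1.00, 0.955 and 0.637), the rule gives −10, +5.7 and +3.8 mL, mean −0.15 mL. This shows that a near-zero mean can be displaced. It does not show that it will be.

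**The case against.** A reader might infer that the rule by itself produces or hides the Day 14 change. The documents do not support that. The same sequence and formula apply at both visits, at one site ("Single-center, prospective, dose-escalation clinical trial"), and a constant gap or shape factor can neither create a change in a subject nor reverse its sign. The false fall of 13.8 mL needs a gap that goes from 0 to 1.5 mm in the same subject, which nothing in the protocol indicates. Even then it moves a group mean by 13.8/3 = 4.6 mL or 13.8/6 = 2.3 mL, and the protocol gives no expected change or SD to set against this. With contiguous slices the gap error is zero. All of this stands.

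A reader might also infer that ABC/2 is valid only for ellipsoids and must be replaced. It is exact for any body that fills half of its A × B × C box, a triangular prism included, so a wedge-shaped infarct is not in itself a failing case. The approximation belongs to a named method, and choosing planimetry instead is a preference between methods. The text does not forbid summing over lesions either. This stands too.

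Last, the consequence is small. The body of the protocol treats the endpoint as exploratory, and section 11(3) assigns it no comparison. The sample size rests on the 3+3 design ("a sample size of 6-18 subjects is sufficient to identify the MTD").

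None of this removes the fault in the written definition of C, or the lack of any requirement to keep slice geometry the same within a subject.

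**Conclusion.** The point holds as a minor correction to a stated rule. As written, C omits the inter-slice gap. For an assumed 5 mm thickness and a gap of 0 to 1.5 mm, volumes and absolute mean changes come out 0% to 23% too small. Percent change is unaffected when the geometry is the same at both visits. If the gap differs, a stable lesion can show a false fall of 7.7% (1.0 to 1.5 mm) to 23% (0 to 1.5 mm), or a false rise in the opposite direction. The fixed coefficient of 0.5 adds a shape error, from none for a triangular prism and about 5% for an ellipsoid to much more for other shapes. Shape differences between subjects or visits can therefore distort a mean over 3 to 6 subjects. Whether any of this occurs depends on acquisition settings and lesion shapes that the protocol does not give. The endpoint is exploratory in section 5(4) and secondary in the synopsis, and it does not enter the DLT definition, escalation or sample size.

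**What to change.** In section 4(3), item 3:
- define C as number of slices × slice spacing (thickness plus gap), read from the image header;
- require the same DWI slice thickness and spacing at each visit for a given subject;
- state that volumes of separate lesions are measured separately and summed.

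This is a change of wording and needs no extra scan.

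Optionally, add slice-by-slice planimetry (outlined area × spacing, summed over slices and lesions) as a sensitivity measure that does not depend on lesion shape. The cost is reading time on at most 18 subjects × 3 scans (baseline, Day 14, Day 90) = 54 scans. The protocol names no reader for infarct volume, so that time would have to be assigned.
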